2.3 Patient disposition, demographics and other baseline characteristics

2.3.1 Patient disposition

The number and percentage of patients enrolled, completed or discontinued from the biomarker sub-study, including reasons for discontinuation will be presented by treatment group for all patients in the BAS dataset.

Descriptive statistics for the background and demographic data will be provided for the BAS dataset. Continuous variables will be summarized using N (the number of subjects in the analysis set), n (the number of subjects with available/imputed value), mean, median, standard deviation, minimum and maximum.

Frequency counts and percentages will be presented for categorical variables for non-missing data. A row (category) denoted “Missing” will be included in count tabulations if a non-zero count of missing values is present. Percentages will be calculated using the number of patients in the relevant population or subgroup as the denominator. If a count of zero is obtained, the zero count and percentage will still be displayed. Two-sided 95% confidence intervals will be evaluated and reported for frequency percentages using Clopper-Pearson / Exact method.

2.3.2 Demographics and other baseline characteristics

The following data will be summarized for BAS dataset:

- age (in years, and year categories ≤ 65 , > 65)
- gender (male/female)
- child bearing status (able to bear children/post-menopausal/sterile - of child bearing age)
- race (Asian/Caucasian/Black or African American/Unknown/Other)
- source of subject referral
- smoking status (never/current/former)
- average pack year (former/current/overall)
- height (cm)
- weight (kg)
- body mass index (BMI) = $\text{weight (kg)} / (\text{height (meters)})^2$
- waist circumference (cm)
- hip circumference (cm)
- waist to hip ratio = $\text{waist circumference (cm)} / \text{hip circumference (cm)}$
- sitting pulse (bpm)
- systolic and diastolic blood pressure (mmHg)

2.4 Treatments (study treatment, rescue medication, concomitant therapies, compliance)

2.4.1 Study treatment / compliance

The number and percentage (%) of patients receiving injections will be summarized categorically (one fewer than all, two fewer than all etc.) for the core study using the BAS set by treatment groups and overall. The duration of exposure (days) to secukinumab study treatment will be presented similarly.

Duration of exposure is calculated as $((\text{last known date of study medication (as per the DAR CRF)} - \text{start date of medication}) + 1) / 7$ (in weeks)

The duration of exposure will be reported in weeks.

Start date and last known date of study medication will be as per the drug accountability record eCRF page.

2.4.2 Prior, concomitant and post therapies

Not applicable.

2.4.3 Study compliance

2.4.3.1 Secukinumab

Compliance as percentage of injections administered will be calculated as the number of injections applied (based on documented study drug administrations and syringe counts as given in the dosage administration record eCRF page) divided by the number of injections scheduled per protocol. For dropouts/discontinuations, the denominator will be adjusted to number of injections scheduled per protocol until discontinuation.

Compliance is given by the formula:

Compliance (%) = $100 * (\text{total no of injections administered}) / (\text{no. of injections prescribed until discontinuation})$

In the core study, two pre-filled syringes containing 150 mg secukinumab will be provided as open label medication at weeks 0, 1, 2, 3, 4, 8, 12, 16, 20 and 24 (last injection is at week 24).

Compliance percentage will be summarized for the BAS dataset (displaying totals) by treatment group and also by categories (< 80% and ≥ 80% to 100%).

2.4.3.2 Lifestyle intervention

Compliance as percentage of lifestyle intervention visits participated in will be calculated as the number of intervention visits attended (based on documented participation counts as given in the lifestyle intervention record eCRF page) divided by the number of lifestyle intervention visits scheduled per protocol until discontinuation. For dropouts/discontinuations, the denominator will be adjusted to number of intervention visits participated scheduled per protocol until discontinuation.

Compliance is given by the formula:

Compliance (%) = $100 * (\text{total no of lifestyle intervention visits participated}) / (\text{no. of lifestyle intervention visits scheduled})$

In the core study, lifestyle intervention visits are scheduled at weeks 0, 1, 2, 3, 4, 8, 16 and 24.

Compliance percentage will be summarized for the BAS dataset (displaying totals) by treatment group and also by categories (< 80% and ≥ 80% to 100%).

2.5 Analysis supporting sub-study objective(s)

2.5.1 Primary endpoint(s)

At baseline (week 0), week 16 and week 28 the following markers will be assessed using fasting blood samples:

- Free fatty acid serum profile
- sThy-1
- Adiponectin
- Leptin
- Insulin
- HOMA-IR
- Proinsulin
- IL-6
- TNF-alpha
- M30 assay
- IL-1 beta
- IL-1Ra
- IL-18
- IL-18bp
- PINP
- CTX
- RANKL
- OPG
- Sclerostin
- NT-proBNP

Free fatty acid serum profile is comprised of total 11 molecules i.e., Free fatty acid, Eicosatrienoic acid, Heptadecanoic acid, Linoleic acid, Linolenic acid, Oleic acid, Palmitic acid, Palmitoleic acid, Pentadecanoic acid, Stearic acid & Tetradecanoic acid. All the molecules will be analyzed separately for Free fatty acid serum profile.

2.5.2 Statistical hypothesis, model, and method of analysis

There will be no formal hypothesis testing in the biomarker sub-study.

All the biomarkers at weeks 0, 16, and 28 will be analyzed analogous to the sub-study endpoint. Absolute biomarker scores will be analyzed using a mixed model for repeated measures (MMRM), with factors treatment, center, visit, visit*treatment interaction and covariate baseline respective biomarker value. The raw as well as the adjusted least square means and

their differences between treatment groups will be calculated for each visit together with their corresponding 95% confidence intervals and p-values.

2.5.3 Handling of missing values/censoring/discontinuations

For all continuous variables, all available measurements will be included in the Mixed Model for Repeated Measures (MMRM).

2.6 Additional analysis

In order to explore the additional effect of lifestyle intervention on biomarker sub-study endpoints, an additional analysis will be performed for all the study biomarkers at V9 (Week 16) & V12 (Week 28) for both treatment arms, separately based on three below mentioned subgroups:

- Patients with weight loss $< 5\%$
- Patients with weight loss $\geq 5\% - < 10\%$
- Patients with weight loss $\geq 10\%$

For all the above mentioned sub-groups, the no. of patients falling in each sub-group will be descriptively summarized using frequency, percentages and exact 95% Clopper-Pearson CI at V9 (Week 16) and V12 (Week 28) for both treatment arms, separately using BAS. Change in weight loss will be compared from the baseline weight.

All the patient's biomarkers value will be summarized descriptively using N, n, mean, median, standard deviation (SD), min and max for all the three subgroups using BAS. Absolute biomarker values will be analyzed using a MMRM with factors treatment, center, visit, visit*treatment interaction and covariate baseline biomarker value. The raw- as well as the adjusted (LS-) means and their differences between treatment groups will be calculated for each visit together with their corresponding 95% confidence intervals and p-values, for all the three sub-groups separately. Also, similar MMRM model will be used for all the biomarkers listed in [section 2.5.1](#), for all the three sub-groups, separately.

All the above- mentioned analyses for all study biomarkers will be performed separately for both treatment groups for below mentioned comparisons:

- a. Patients with weight loss $\geq 5\% - < 10\%$ vs. Patients with weight loss $< 5\%$
- b. Patients with weight loss $\geq 10\%$ vs. Patients with weight loss $< 5\%$
- c. Patients with weight loss $\geq 5\% - < 10\%$ vs. Patients with weight loss $\geq 10\%$

2.6.1 Laboratory data

Clinically significant abnormal laboratory values will also be assessed for the following parameters of the biomarker sub-study (only for patients participating in the biomarker sub-study): Adiponectin, leptin, insulin, HOMA-IR, proinsulin, IL-6, TNF-alpha, M30 assay, NT-proBNP.

3 Sample size calculation

There is no formal sample size computation for the sub-study.

4 Change to protocol specified analyses

- i. Creation of BAS
- ii. Reporting of patient disposition, demographics and baseline characteristics as defined in [section 2.3](#)
- iii. Reporting of study treatment compliance and study compliance as mentioned in [section 2.4](#)
- iv. Additional analysis proposed for stratification of the analysis for all study biomarkers by the groups “patients achieving weight loss <5%”, “patients achieving weight loss \geq 5% - <10%” and “patients achieving weight loss \geq 10%” in each treatment arm.

5 Appendix

5.1 Statistical models

MMRM Model

Absolute biomarkers value will be analyzed using a Mixed Model for Repeated Measurements (MMRM) with factors treatment, center, visit, visit*treatment interaction and covariate baseline biomarker value.

```
proc mixed data = BAS covtest;  
class subjid TRT01P siteid avisitn;  
model CHG_B = base TRT01P siteid avisitn avisitn*TRT01P/ ddfm=KR  
residual;  
repeated avisitn / type=un subject=subjid rcorr;  
estimate "Trt diff at Week 28" Trt 1 -1 TRT01P*avisitn 1 -1/cl;  
lsmeans Trt*VisitWk / cl;  
run;
```

Where,

BAS = dataset; TRT01P = Treatment arms (A & B); CHG_B = Change from Baseline

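### The biomarker SAP's MMRM code cannot produce the Week 28 treatment difference it is labelled as, nor the by-visit differences the text promises

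*SAP*

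**What the plan says.** All references here are to the biomarker sub-study SAP.

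- **Target.** Section 2.5.2 plans an MMRM with treatment, center, visit, visit-by-treatment interaction and the baseline value of the marker. It promises raw and adjusted means and their between-arm differences at each visit, with 95% confidence intervals and p-values. It also rules out formal hypothesis testing.
- **Code, Section 5.1.** The classification statement is "class subjid TRT01P siteid avisitn", the model is "model CHG_B = base TRT01P siteid avisitn avisitn*TRT01P/ ddfm=KR" and the covariance is "repeated avisitn / type=un subject=subjid rcorr". The results are then requested by "estimate 'Trt diff at Week 28' Trt 1 -1 TRT01P*avisitn 1 -1/cl" and "lsmeans Trt*VisitWk / cl".
- **Legend, Section 5.1.** "BAS = dataset; TRT01P = Treatment arms (A & B); CHG_B = Change from Baseline". Nothing else is defined.
- **Visits.** Section 2.5.2 says "All the biomarkers at weeks 0, 16, and 28 will be analyzed analogous to the sub-study endpoint". Section 2.6, which uses a model of the same form in weight-loss subgroups, names only Weeks 16 and 28.
- **Response.** The prose of 2.5.2 and 5.1 says the absolute marker value is modelled. The code models `CHG_B`, the change from baseline.

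**The concern.** The ESTIMATE and LSMEANS lines are the two statements that should turn the fitted model into the treatment comparison. They use names that the model does not contain, and the interaction coefficients do not pick out Week 28 in either arm. Even with the names corrected, the LSMEANS line would print adjusted means without the differences that Section 2.5.2 promises.

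This is the only model code in the document. Section 2.5.1 lists 19 single markers plus 11 fatty-acid molecules that are to be analysed separately, so it serves 19 + 11 = 30 outcomes, before the subgroup repeats in Section 2.6. At stake is whether the specified program yields the planned result. If it does not, the repair is left to whoever runs it, after the plan has been finalised.

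**Working it through.** **1. Names.** The CLASS statement holds `subjid`, `TRT01P`, `siteid` and `avisitn`. The MODEL effects are `base`, `TRT01P`, `siteid`, `avisitn` and `avisitn*TRT01P`. `Trt` and `Trt*VisitWk` are not among them and are not in the legend. Taken literally, the two result statements cannot run.

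**2. What a valid contrast needs.** Read `Trt` as `TRT01P`. Leaving out terms common to both arms (intercept, baseline, site), the mean for arm t at visit v is

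μ(t,v) = α(t) + β(v) + γ(t,v).

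A contrast Σ c(t,v) μ(t,v) has coefficient c(t,v) on γ(t,v), Σ over v of c(t,v) on α(t), and Σ over t of c(t,v) on β(v). A written vector that breaks these sums is not estimable. The Week 28 difference is

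α(A) − α(B) + γ(A,28) − γ(B,28).

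**3. The printed coefficients, visits 16 and 28.** The treatment part is 1, −1. The interaction part is 1, −1, with the remaining cells zero.

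- *Printed CLASS order* (arm, then visit: A16, A28, B16, B28). The interaction part is γ(A,16) − γ(A,28). It requires α(A) = 1 + (−1) = 0, but 1 is written. It requires α(B) = 0, but −1 is written. It requires β(16) = 1 and β(28) = −1, but 0 and 0 are written. The function is non-estimable.
- *Visit-first order* (A16, B16, A28, B28). The interaction part is γ(A,16) − γ(B,16). It requires α(A) = 1, α(B) = −1 and β(16) = 1 − 1 = 0, all as written. The function is estimable and equals the Week 16 difference.

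**4. Numerical check.** The over-parameterised design matrix was built and the printed vector tested for estimability. It was then evaluated with assumed A−B differences of 0, +2 and +5 at Weeks 0, 16 and 28. These values serve only to show which visit is returned.

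| Visits in the model | Interaction order | Printed contrast returns |
|---|---|---|
| 16, 28 | arm, then visit (as printed) | non-estimable |
| 0, 16, 28 | arm, then visit (as printed) | non-estimable |
| 16, 28 | visit, then arm | +2 (Week 16) |
| 0, 16, 28 | visit, then arm | 0 (Week 0) |

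None returns +5. That the software orders interaction columns by the CLASS statement is knowledge of the software, not of the documents. The conclusion does not depend on it, because both orders were tried.

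**5. Coefficients that work.** In the printed order with Weeks 16 and 28, the interaction part 0 1 0 −1 gives α(A) = 0 + 1 = 1, α(B) = 0 − 1 = −1, β(16) = 0 and β(28) = 1 − 1 = 0. It is estimable and returns +5.

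**6. Absolute value or change.** With baseline as a covariate and only post-baseline visits as outcome, subtracting baseline from the response lowers the common baseline slope by 1 and leaves every between-arm difference unchanged. The raw and adjusted means themselves do change scale, so the text and the code describe different tables of means.

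**The case against.** The strongest reply is that nothing misleading is likely to be reported. The sub-study has no formal testing, the prose of Section 2.5.2 states the right target, and a competent programmer can recover the intended output from it. The printed code stops on the undefined names, and after the obvious renaming the printed order gives a non-estimable result and no number. All of that stands and limits the size of the point. It does not make the code correct.

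Two stronger readings are tempting.

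- *A Week 16 result would be printed under a Week 28 label without anyone noticing.* This needs a reordering of the CLASS variables that the plan does not contain, and it needs Week 0 to be absent from the model. It is a possible consequence of an improvised repair, not of the specification.
- *Week 0 is modelled as an outcome, so the covariance becomes singular and baseline adjustment is lost.* The documents do not establish this. The coded response is change from baseline. Section 2.1.1 defines that as post-baseline minus baseline, and Section 2.1.1.2 counts as post-baseline for efficacy only assessments after Visit 2. On those definitions no Week 0 response exists. Section 2.6 names only Weeks 16 and 28. Against that, Section 2.5.2 lists Week 0 among the visits analysed, the prose speaks of absolute values, Table 5-1 lists Baseline as an analysis visit, and the code has no explicit exclusion. What remains is conflicting wording that needs one clarifying sentence. Any estimate of lost precision would need Week 0 to be kept, the fit to converge, and correlations that no document gives, so none is offered.

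**Conclusion.** The point holds for the code. As printed, the two result statements refer to effects that are not in the model. After renaming, the contrast is non-estimable in the printed order and is not the Week 28 difference in any order. Without DIFF, the by-visit differences of Section 2.5.2 are not produced. This rests on reading `Trt` as `TRT01P` and on the model exactly as written. It needs no assumption about effect size, correlation or sample size.

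The wording on Week 0 and on absolute value against change is an inconsistency to reconcile, not a demonstrated modelling error.

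The size is small. The sub-study is exploratory, the failure would most likely be visible, and the primary PASI90 analysis is untouched. It is still a definite error in the only model code of this SAP.

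**What to change.** In Section 5.1, replace the ESTIMATE and LSMEANS lines by `lsmeans TRT01P*avisitn / diff cl`. With two arms and two visits this gives 4 × 3 / 2 = 6 pairwise differences. State that the two between-arm ones, at Week 16 and at Week 28, are reported, and in which direction. Alternatively, keep an ESTIMATE for Week 28 with `TRT01P 1 -1 TRT01P*avisitn 0 1 0 -1`, valid for the printed CLASS order with only Weeks 16 and 28 as outcome visits.

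In Section 2.5.2, state that the MMRM outcome visits are Weeks 16 and 28 and that the Week 0 value enters only as the covariate. In 2.5.2 and 5.1, make the text and code agree on whether the response is the absolute value or the change from baseline. Either gives the same treatment differences once Week 0 is excluded as an outcome.

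The cost is two lines of code, one sentence and one consistent term for the response. No data collection, sample size or other analysis changes.

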5.2 Visit windows and mapping of visits

Visit-windows will be used for biomarker sub-study data that is summarized by visit; they are based on the study assessment schedule and comprise a set of days around the nominal visit day. For any assessment there will be a visit window to cover the complete range of days within the study. So, the overlapping visit window period will be used for the analyses, as mentioned below in [Table 5-1](#).

Table 5-1 Assessment windows for scheduled visits

Analysis Visit	Week	Scheduled Day	Visit Window
Baseline	0	1	-28 days to Day 1
Week 16	16	113	Day 99-127
Week 28	28	197	Day 183-225

Clinical Development

CAIN457A/METABOLYX

CAIN457ADE08

A randomized, multicenter 28 week study to compare the efficacy and safety of combining Cosentyx (Secukinumab) (4 weekly, 300 mg s.c.) with a lifestyle intervention to Cosentyx therapy alone in adult patients with moderate to severe plaque type psoriasis and concomitant metabolic syndrome, followed by a 28 week extension period

Extension Period Statistical Analysis Plan (SAP)

Document type:	SAP Documentation
Document status:	Addendum 1.0
Release date:	19-Sep-2022
Number of pages:	21

Property of Novartis
Confidential
May not be used, divulged, published or otherwise disclosed
without the consent of Novartis

Template Version 4.0, Effective from 23-Apr-2021

Document History – Changes compared to previous final version of SAP

Date	Time point	Reason for update	Outcome for update	Section and title impacted (Current)
27-Jul-2022	Prior to DB lock	Creation of final version	N/A - First version	NA
19-Sep-2022	After Final DB lock	Creation of Addendum version 1.0	Text modified in section 2.6.1	2.6.1

Table of contents

Table of contents	3
List of abbreviations	5
1 Introduction	6
1.1 Study design.....	6
1.2 Study objectives and endpoints	7
2 Statistical methods.....	8
2.1 Data analysis general information	8
2.1.1 General definitions	8
2.2 Analysis sets	8
2.3 Patient disposition, demographics, and other characteristics	8
2.3.1 Patient disposition	8
2.3.2 Demographics and other characteristics.....	9
2.4 Treatments (study treatment, rescue medication, concomitant therapies, compliance).....	9
2.4.1 Study treatment / compliance.....	9
2.4.2 Study Compliance	9
2.4.3 Concomitant and post therapies	10
2.5 Analysis supporting study objective(s).....	10
2.5.1 Endpoint(s).....	10
2.5.2 Statistical hypothesis, model, and method of analysis.....	11
2.5.3 Handling of missing values/censoring/discontinuations.....	11
2.6 Safety analyses.....	11
2.6.1 Adverse events (AEs).....	11
2.6.2 Deaths.....	12
2.6.3 Laboratory data	12
2.6.4 Other safety data	12
2.7 Patient-reported outcomes	13
2.8 Interim analysis.....	13
3 Sample size calculation	13
4 Change to protocol specified analyses	13
5 Appendix	14
5.1 Imputation rules	14
5.1.1 AE date imputation	14
5.1.2 Concomitant medication date imputation	16
5.2 Statistical models.....	18

5.3	Patient reported outcomes (PRO)	18
6	Visit windows and mapping of visits	20
7	Reference.....	21

List of abbreviations

AE	Adverse Event
ALT	Alanine Aminotransferase
AST	Aspartate Aminotransferase
ATC	Anatomical Therapeutic Classification
CI	Confidence interval
CRF	Case Report Form
CSR	Clinical Study Report
DLQI	Dermatology Life quality index
FAS	Full Analysis Set
HbA1c	Hemoglobin A1c
HDL	High-density lipoprotein
HRQoL	Health-related quality of life
IA	Interim Analyses
LDL	Low-density lipoprotein
LLN	Lower Limit of Normal
LOQ	Limit of Quantification
PPS	Per-Protocol Set
PRO	Patient-reported Outcomes
PT	Preferred Term
RAP	Reporting & Analysis Process
SAE	Serious Adverse Event
SAF	Safety Analysis Set
SAP	Statistical Analysis Plan
SAS	Statistical Analysis System
SD	Standard Deviation
SOC	System Organ Class
ULN	Upper Limit of Normal
WHO	World Health Organization

[figure not shown]
1 Introduction

The purpose of the Statistical Analysis Plan (SAP) is to describe the implementation of the statistical analysis for extension period as planned in section 9.7 in the clinical study protocol version 02 for the clinical trial CAIN457ADE08 (METABOLYX). Additional analyses, specifications or deviations from the study protocol planned before database lock will also be discussed in this SAP.

1.1 Study design

This study is a randomized, open-label, parallel-group, active comparator-controlled trial with two treatment arms. The design is shown in [Figure 1-1](#).

Figure 1-1 Study Design

R: Randomization

[figure not shown]
* During the extension period the lifestyle intervention can be continued by patients who have been in arm B during the core study, or it can be started by patients who have been in arm A. Participation in the lifestyle intervention during the extension period is **not** mandatory.

†Participation in the extension period itself is mandatory. Psoriasis treatment during the extension period can be chosen freely by the Investigator. No study drug is supplied during the extension period.

Extension period: After 28 weeks the study continues with an extension period, during which lifestyle intervention is offered to all patients, irrespective of their prior treatment arm. This means that patients of arm B, who are willing to, can continue their previously started lifestyle intervention program and patients of arm A, who are willing to, can start the lifestyle intervention program at the beginning of the extension period. **All patients, irrespective of their decision whether to start/ continue lifestyle intervention or not, have to participate in the extension period and visit their dermatologic study center for scheduled visits.** The extension period ends at week 56, where all patients complete the study. There will be no study

drug supply during the extension period. The treating physician can choose psoriasis therapy freely according to his/her discretion.

